Working Title:

A Pilot Translational Study of Varenicline Sampling to Promote Treatment Engagement and Smoking Cessation

Principal Investigator

[name]

Co-Investigators:

[name]

[name]

[name]

[name]

[name], MS

Plus all people within my team: including [name]

Specific Aims

Smoking cessation remains the primary goal for population-based tobacco control. Many smokers lack intrapersonal resources to initiate and succeed in a sustained quit attempt. Whether lacking in motivation or confidence, or holding misbeliefs that undermine use of evidence-based medications, or through lack of decisional autonomy, many smokers show “cessation fatigue” after repeated failures and remain simply unable or unwilling to quit. Our research program has been addressing these barriers for the past 10 years, focusing on concrete, behavioral tools to overcome each. A number of cessation treatments (both pharmacologic & behavioral) have been available to smokers for some time, but their access and reach are often restricted, and consequently are under-used. We believe that new methods are needed to not only develop new cessation treatments (not our focus here), but also to innovate new methods for how existing treatments get disseminated into the real world for a larger, deeper penetrance. This is our focus herein.

Guided by recommendations for pragmatic interventions (i.e., brief, readily acceptable, easily disseminated), our team has developed and tested interventions that are face valid, easily delivered, practical, and broadly applicable. This work began 10 years ago with a large (N=849) nationwide, population based randomized clinical trial testing the concept of nicotine replacement therapy (NRT) sampling. As applied to a broad population of smokers, inclusive of those wanting and not wanting to quit, sampling provides a concrete, behavioral catalyst to induce quit attempts and quitting. NRT sampling was hypothesized to increase self-efficacy and motivation, and to familiarize smokers with and facilitate positive attitudes toward medication. Our prior trial consisted exclusively of smokers unmotivated to quit, who were given (or not) samples of NRT with minimal adjunctive support. Our positive results received widespread prominence, including high tier publication (*Archives of Internal Medicine*). In separate trials, we further developed the concepts and delivery of medication sampling. This included a small pilot trial (N=157) to isolate the importance of smoker motivation to quit, within a sample of smokers across South Carolina, which demonstrated the beneficial effects of sampling across the motivational spectrum. Finally, we have an ongoing trial to examine NRT sampling in primary care settings across South Carolina (20 clinics; N=1243 participants), our most applied and real-world test of sampling to date. Recruitment and follow-up will conclude in summer 2018, and we look forward to forthcoming results.

Our prior work on NRT sampling creates a compelling question as to whether varenicline sampling would have similar, or better, effects. Varenicline is inarguably the strongest single cessation medication available, superior to other single options. As a prescription medication, whether varenicline is suitable for sampling is unclear. On one hand, haphazard use, over a brief time, may not deliver sufficient pharmacologic benefit. Prescription delivery incurs its own barriers to widespread delivery (which can be overcome). On the other hand, much like NRT sampling, it could provide a tangible cue to action that provides psychological engagement (motivation, confidence, autonomy) to sustain subsequent use and ultimately enhance cessation. Whereas many smokers have negative reactions against NRT, varenicline might be a suitable alternative. Indeed, we ourselves are a bit mixed as to whether varenicline sampling has any clinical potential, but either way, we think it is an interesting and compelling question that offers both clinical and regulatory implications, and thus deserves further testing.

A large-scale trial of varenicline sampling is premature, largely because we do not know if this is even viable. We therefore propose a pilot clinical trial with **primary aims** to: 1) determine feasibility (recruitment, compliance, retention), 2) further evaluate our hypothesized mechanisms (some from our NRT work but others new), and 3) assess preliminary effect sizes, all of which would guide a subsequent trial. We will recruit 100 smokers across our state and randomize them to receive a 4-week sample of varenicline, or not, and will follow all for 3 months. Our statewide focus derives from our hands-off (i.e., translatable) intent, such as would be eventually implemented in busy real world clinical practice (eg. primary care), yet our methods include daily diary assessment to enhance rigor. We are mindful of requirements for physician oversight, and embed full precautions for safety. Our study sample will include smokers both wanting to quit and not (purposeful recruitment of each, with stratified randomization), which will allow for exploratory sensitivity analyses to assess the role of smoker motivation on outcomes. We hypothesize that: 1) varenicline sampling will be feasible to deliver (efficient recruitment among all-comer smokers) with reasonable compliance (>80% of study sample using meds on at least 50% of sampling period), with 2) greater relative increases in all hypothesized mediators, and 3) greater increases in a range of cessation-related behavior: a) further treatment engagement (i.e., further medication use, calls to quitline), b) quit attempts, c) cessation. We are underpowered for tests of mediation and for cessation outcomes. Nonetheless, these effect sizes, as well as the larger lessons learned from this pilot RCT, will guide a larger trial. If varenicline sampling were to show promise through this and future trials, this would offer great dissemination appeal to physicians, quitlines, etc. in that, much like our NRT work, varenicline sampling could be a **pragmatic strategy to engage more smokers in better treatments, sooner**.

Human Subjects Research

1. Risks to Human Subjects

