1.1 Human Subjects Involvement and Characteristics

Eligibility criteria include:

- 1) age 18+;
- 2) daily smoker (25+ days per previous month);
- 3) smoking 5+ cigarettes/day;
- 4) smoking \geq 1yr;
- 5) some interest in eventual quitting (>2 on 10-point scale);
- 6) has a primary care doctor and has seen that doctor at least once in past year;
- 7) not currently pregnant, breastfeeding, or planning to become pregnant;
- 8) no suicidal ideation in past month, nor any lifetime suicide attempt;
- 9) no reports of hallucinations;
- 10) no reports of history of seizures; and
- 11) own a smartphone or have regular (daily) access/use of email.
- 12) if female, willing to take a pregnancy test
- 13) not currently taking any medications to help quit smoking
- 14) no diagnosis of schizophrenia or bipolar disorder
- 15) no members of the same household currently enrolled in the study

Participants will be recruited from the general community, across South Carolina, using print/online advertising, including social medial. We intend to enroll an Intent-to-Treat sample of 100 participants, comprised of 50% female, and at least 30% African American smokers. However, a number of consented participants will not necessarily enroll in the trial (defined as completing initial/Week 0 phone call) and thus we plan for 120 consented participants. No more than 100 will enroll.

TARGETED/PLANNED ENROLLMENT: Number of Subjects			
Racial Categories	Sex/Gender		
	Females	Males	Total
American Indian/Alaska Native	0	0	0
Asian	0	0	0
Native Hawaiian or Other Pacific Islander	0	0	0
Black or African American	20	20	40
White	40	40	80
Racial Categories: Total of All Subjects*	60	60	120

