2.1 Recruitment and Informed Consent

All research personnel have up to date CITI Certification for Protection of Human Subjects, and will keep this training current throughout the course of the study. Study participants will be recruited through statewide media outlets, including social media. Potential participants will be screened online (redcap survey) to determine study eligibility. Eligible participants will provide contact information, and either receive (their preference) 1) a mailed packet with consent form (2 copies), baseline survey, along with postage paid return envelope, or 2) doxy.me teleconsent. We have used each of these consenting options in our prior and ongoing trials. On all

correspondence with potential participants, we provide our toll-free number if any questions or problems arise. A returned, signed consent form will comprise the consented sample; in the past, about 45-50% of individuals who are mailed a consent return it; we do not badger those who decline. However, not all consenting individuals are able to be reached (~10% from previous studies) and those that are (~90%) will comprise the intent-to-treat enrolled sample. Thus, to reach our intended sample of 100 enrollees, we plan for consent of up to 120 consented. We will abide by all HIPAA regulations as set forth by our institution. The PI will supervise all aspects of the recruiting process.

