Only study team members who are involved in recruitment and data collection will have access to PHI. We will use the participant's name and phone number for prescreening documents, which will be stored in a password protected file on a secure network drive at MUSC. Subject names and numbers will be deleted from the file at the close of the study (after analyses are complete).

3. Potential Benefits of the Proposed Research to the Participants and Others / Importance of the Knowledge to be Gained

As for benefit to study enrollees, all participants will receive a referral to the SC Quitline, an evidence-based, free, and anonymous service. Half of the participants will receive a 1 month supply of varenicline, inarguably the best available cessation medication. We do expect higher rates of treatment engagement, and cessation-related behavior (quit attempts, abstinence) among those who receive varenicline.

4. Importance of Knowledge to be Gained

We have previously shown the pragmatic value of medication sampling as a method to get more smokers to make better quit attempts sooner. Whether the same rationale applies for varenicline is unclear. It would be a leap to suggest that varenicline sampling would compare to NRT sampling, and this is the very reason why this proposal offers innovation. Indeed, if varenicline sampling is found not effective to promote quitting, then this would suggest: a) sampling should be restricted to OTC products, b) sampling should be restricted to products that do not have rigid instructions for administration, and/or c) physician guidance is needed for varenicline use. In contrast, if varenicline sampling does show promise, then this would further demonstrate that minimal provider involvement is adequate, which further diminishes barriers to access. Either way, we believe this is an important research question and will answer some important questions for our field. We are unaware of any randomized controlled trial that tests varenicline sampling. Much like our prior work on NRT sampling, we believe that varenicline sampling will be a catalyst for cessation, motivating more smokers to make better, evidence-based quit attempts sooner.

5. Data and Safety Monitoring Plan

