5.1 Summary of the Protocol

This application proposes a pilot RCT to determine the feasibility of varenicline sampling, as well as assess early determinants of intervention mechanism and effect sizes as compared to non-sampling control condition. Adult smokers (N=100 enrollees, up to 120 consented) from across South Carolina will be recruited via print and social media outlets. With the exception of varenicline medication, our methods strictly adhere to our prior RCTs of NRT sampling, also done remotely. Thus, a central focus here is whether varenicline sampling, as delivered remotely, is feasible to do. Participants will be screened for eligibility criteria, more conservatively than prior RCTs, including seminal EAGLES trial. Upon consent, they will be randomized to receive a one-time, 4-week sample of varenicline (.5mg tablets, 56 tablets maximum) or not. The selected dosage balances competing perspectives to: a) provide maximum therapeutic benefit, while b) not imposing undo confusion of escalating with varying dosages, and c) giving the participant ultimate choice of use. All participants are asked to complete daily diaries during the sampling period, and follow-up assessments will continue for 12 weeks beyond study enrollment. As a pilot study, our main focus is on 1) feasibility: operationally defined as: a) efficiency of recruitment (goal: 5/month, b) use of medication (incidence, quantity, patterns of use), and c) adverse events, 2) Mechanisms include measures of motivation, confidence, knowledge of and attitudes toward medication, autonomy to quit, expectancies, and cessation fatigue, and 3) early estimation of treatment effect size (cessation related-outcomes: quit attempts, medication conversion), all of which will inform a larger trial.

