5.4. Quality Assurance

The REDCap system has validation options to not accept outliers, illogical response patterns, etc. The PI will have weekly meetings with the research assistants to discuss qualitative comments received during data collection and any problems in data collection. The statistician will periodically examine the database to look for irregularities. Initial data analyses will examine distributions of variable scores, comparability of baseline characteristics, follow-up rates and use of extra-study cessation treatment across conditions in case analyses need to be adjusted for these.

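### The available text does not fix adjustment for the motivation stratum or the baseline mediator score in advance; it offers only adjustment after differences are seen, at some cost in precision

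*Combined protocol and SAP*

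**What the plan says.** - **Strata.** The Specific Aims describe recruiting smokers who do and do not want to quit: "purposeful recruitment of each, with stratified randomization), which will allow for exploratory sensitivity analyses to assess the role of smoker motivation on outcomes". No other analytic use of the strata appears in the text available.
- **Mediators.** The Specific Aims hypothesise "greater relative increases in all hypothesized mediators". Section 5.1 lists them: "Mechanisms include measures of motivation, confidence, knowledge of and attitudes toward medication, autonomy to quit, expectancies, and cessation fatigue". Motivation is therefore both the stratification factor and a mediator. No model is named.
- **Baseline data.** Section 2.1 mentions "a mailed packet with consent form (2 copies), baseline survey, along with postage paid return envelope". The contents of that survey are not itemised. The hypothesis of increases implies baseline mediator values.
- **Adjustment.** Section 5.4 says that the initial analyses will examine "comparability of baseline characteristics, follow-up rates and use of extra-study cessation treatment across conditions in case analyses need to be adjusted for these".
- **Size and purpose.** Section 1.1: "We intend to enroll an Intent-to-Treat sample of 100 participants". Section 3: "Half of the participants will receive a 1 month supply of varenicline". That gives about 50 per arm. Preliminary effect sizes are the third primary aim, and the Specific Aims concede low power for mediation and cessation.
- **Where the analysis plan lies.** Section 5.3 refers to Section C3f, which is not part of the document supplied.

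**The concern.** Two things are at stake.

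**The model depends on the data.** Under Section 5.4, whether and for what to adjust is settled after the arms have been compared. Two of the three candidates, follow-up rates and use of outside cessation treatment, arise after randomisation. Outside treatment also overlaps an outcome: the Specific Aims count further medication use and quitline calls as treatment engagement. If sampling leads people to seek more treatment, adjusting quit attempts or abstinence for that treatment could remove part of the effect being estimated.

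**Precision.** Estimates from about 50 per arm are meant to guide a larger trial. The stratum is known for everyone randomised, and baseline mediator scores appear to be collected. Leaving them out of the main comparisons would give wider intervals than the design allows, wherever they predict the outcome.

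**Working it through.** **A figure to reproduce.** There is none. The documents give no alpha, power, effect size, SD, event rate, baseline to follow-up correlation or target interval width. Only the sample size comes from the documents: 100 enrolled, half given varenicline, so 50 per arm. The correlations, R² values and stratum rates below are assumptions.

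**1. Mediators: change score against baseline-adjusted score.** Take equal SDs at baseline and follow-up, correlation rho, full retention, and units of one SD.

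- Variance per person, change score: 2(1 − rho)
- Variance per person, follow-up adjusted for baseline: 1 − rho²
- Ratio: (1 − rho²) / [2(1 − rho)] = (1 + rho)/2, which is at most 1
- 95% half-width: 1.96 × √(2 × variance / 50)

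At rho = 0.5, change score: 1.96 × √(2 × 1.00/50) = 0.392. Adjusted: 1.96 × √(2 × 0.75/50) = 0.339.

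| Assumed rho | Change score | Adjusted | Narrower by |
|---|---|---|---|
| 0.3 | 0.464 | 0.374 | 19.4% |
| 0.5 | 0.392 | 0.339 | 13.4% |
| 0.7 | 0.304 | 0.280 | 7.8% |
| 0.9 | 0.175 | 0.171 | 2.5% |

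At 40 per arm the half-widths grow (0.519 and 0.418 at rho = 0.3), but the percentages do not change. The formula ignores the small cost of estimating the slope.

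**2. Continuous outcomes: adding the stratum.** If the stratum explains a share R² of the variance, the half-width is multiplied by √(1 − R²). For assumed R² of 0.02, 0.10 and 0.20 it narrows by 1.0%, 5.1% and 10.6%. These are gains from the stratum alone; where the baseline score is already in the model, the stratum may add less.

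**3. Binary outcomes: risk difference.** Take two equal strata, so 25 per arm in each and equal Mantel-Haenszel weights. Assume rates of 20% and 40% in control, and 30% and 60% with sampling. The pooled rates are 30% and 45%.

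- Unstratified variance: (0.30 × 0.70 + 0.45 × 0.55)/50 = 0.4575/50 = 0.00915; half-width 0.187
- Stratified variance: 0.25 × (0.16 + 0.24 + 0.21 + 0.24)/25 = 0.00850; half-width 0.181
- Narrower by 3.6%

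| Assumed control rates | Assumed sampling rates | Unstratified | Stratified | Narrower by |
|---|---|---|---|---|
| 3%, 10% | 6%, 20% | 0.116 | 0.114 | 1.8% |
| 10%, 30% | 20%, 40% | 0.169 | 0.164 | 2.7% |
| 20%, 40% | 30%, 60% | 0.187 | 0.181 | 3.6% |
| 5%, 25% | 10%, 40% | 0.156 | 0.147 | 5.3% |
| 20%, 60% | 30%, 75% | 0.194 | 0.175 | 9.7% |

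**4. Binary outcomes: log odds ratio.** In the worked example the standard error is 0.420 unadjusted and 0.436 adjusted for stratum. It rises because the conditional odds ratio is a different estimand. The gain in step 3 belongs to the difference scale.

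**The case against.** The strongest reply is that the governing text has not been seen. Section 5.3 places the analysis plan in Section C3f, and the reference list includes a paper on statistical analysis of longitudinal tobacco trials with dichotomous outcomes that the available text does not cite. C3f may already fix these covariates. This stands: the point can only be that no available text does so.

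Four stronger readings are tempting, and the documents do not support them.

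- **That mediators will be judged by raw change scores.** The wording about increases is a hypothesis. A baseline-adjusted model would test it equally well, so the gains in step 1 apply only if change scores are planned.
- **That the main comparisons will leave the strata out.** The Specific Aims say what stratification will allow. They do not exclude other uses.
- **That every arm difference would have an overstated standard error.** This needs a stratum that predicts the outcome and a difference scale. The documents give no stratum-specific rates and name no effect scale. Eligibility requires a score above 2 on a 10-point interest scale, which may bring the strata closer together.
- **That the results would be invalid.** The arms are randomised, so leaving out a baseline covariate does not bias the difference, and an interval that ignores predictive strata errs on the wide side.

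It is also fair to say that this is a pilot with no stated efficacy threshold or precision target, and that the gains are modest. That limits the weight of the point. It does not answer the concern about choosing covariates after comparing the arms, or about having a post-randomisation variable among the candidates.

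**Conclusion.** The point holds as one of precision and prespecification. The available text names only an exploratory use of the strata, and its sole adjustment rule is triggered by what the data show. Nothing available commits to the stratum or the baseline mediator score, and the content of C3f is unknown.

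The size rests on assumed inputs. Mediator intervals would be about 8% to 19% narrower for correlations of 0.7 down to 0.3, and 2.5% at 0.9, conditional on change scores being the alternative and on the mediator having been measured at baseline. Risk-difference intervals would be about 2% to 10% narrower across the five sets of stratum rates tried, with no such gain for log odds ratios. The gains are modest, but they bear on a primary aim and cost almost nothing.

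**What to change.** State in the analysis plan, or confirm that Section C3f already states, that:

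1. arm comparisons include the motivation stratum used in randomisation;
2. each mediator measured at baseline is analysed by regressing the follow-up score on arm, baseline score and stratum;
3. quit attempts, treatment engagement and abstinence are reported as stratum-weighted (Mantel-Haenszel) risk differences with 95% confidence intervals;
4. these covariates are fixed in advance, whatever the baseline table shows;
5. the main effect estimates are not adjusted for cessation treatment obtained outside the study after randomisation. Its use by arm can be reported descriptively.

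Section 5.4 should be reworded to agree, keeping the comparability checks as description and not as a trigger for adjustment. The cost is a few sentences. No new data are needed for the stratum, or for mediators already in the baseline survey; the survey's contents should be checked against the mediator list in Section 5.1.

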1.1 Human Subjects Involvement and Characteristics

Eligibility criteria include:

- 1) age 18+;
- 2) daily smoker (25+ days per previous month);
- 3) smoking 5+ cigarettes/day;
- 4) smoking \geq 1yr;
- 5) some interest in eventual quitting (>2 on 10-point scale);
- 6) has a primary care doctor and has seen that doctor at least once in past year;
- 7) not currently pregnant, breastfeeding, or planning to become pregnant;
- 8) no suicidal ideation in past month, nor any lifetime suicide attempt;
- 9) no reports of hallucinations;
- 10) no reports of history of seizures; and
- 11) own a smartphone or have regular (daily) access/use of email.
- 12) if female, willing to take a pregnancy test
- 13) not currently taking any medications to help quit smoking
- 14) no diagnosis of schizophrenia or bipolar disorder
- 15) no members of the same household currently enrolled in the study

Participants will be recruited from the general community, across South Carolina, using print/online advertising, including social medial. We intend to enroll an Intent-to-Treat sample of 100 participants, comprised of 50% female, and at least 30% African American smokers. However, a number of consented participants will not necessarily enroll in the trial (defined as completing initial/Week 0 phone call) and thus we plan for 120 consented participants. No more than 100 will enroll.

TARGETED/PLANNED ENROLLMENT: Number of Subjects			
Racial Categories	Sex/Gender		
	Females	Males	Total
American Indian/Alaska Native	0	0	0
Asian	0	0	0
Native Hawaiian or Other Pacific Islander	0	0	0
Black or African American	20	20	40
White	40	40	80
Racial Categories: Total of All Subjects*	60	60	120

